the course of illness development, as well as individuals who might not otherwise come into contact with traditional referral sources. In response to this challenge, Northwell Health's early psychosis research team is collaborating with Strong365, a nonprofit initiative dedicated to raising early psychosis intervention awareness, to develop and test a proactive and targeted comprehensive digital media marketing campaign designed to facilitate help-seeking and encourage treatment initiation in prospective patients with FEP and their caregivers. Our team will take advantage of search engine advertising, which allows advertisers (researchers) to select keywords/phrases and create linked advertisements appearing as a strategically placed search result. Our dedicated ads will appear in response to online search queries conducted by prospective patients and their caregivers throughout New York State (NYS) that align with the campaign's pre-selected keywords/phrases. Individuals who click on the ads will be immediately directed to our campaign landing page/website, and offered a variety of established, innovative, and interactive online engagement tools intended to instantly connect users with coordinated specialty care (CSC) staff and to facilitate earlier treatment initiation.

Campaign referrals will be centralized and individuals with FEP will be enrolled into OnTrackNY (OTNY), a network of 21 dedicated early psychosis intervention programs throughout NYS. The campaign will target individuals as well as their friends, family, and caregivers, searching for information online. We will measure the DUP of individuals enrolled into OTNY before and after campaign activation and track the impact of the campaign on the number of FEP referrals and number of patients admitted to OTNY in NYS. Furthermore, we aim to identify the campaign target audience most effective at promoting treatment initiation as well as the online tools and resources most effective at encouraging treatment initiation of identified individuals with FEP. We will additionally explore the online trajectories to care of individuals with FEP engaging with the campaign.

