11. RESEARCH PROCEDURES

- Include a detailed description of all procedures to be performed on the research subject and the schedule for each procedure.
- *Include any screening procedures for eligibility and/or baseline diagnostic tests*
- Include procedures being performed to monitor subjects for safety or minimize risks
- *Include information about drug washout periods*
- If drugs or biologics are being administered provide information on dosing and route of administration
- Clearly indicate which procedures are only being conducted for research purposes.
- If any specimens will be used for this research, explain whether they are being collected specifically for research purposes.
- Describe any source records that will be used to collect data about subjects
- *Indicate the data to be collected, including long term follow-up*

We will develop and test two comprehensive digital media campaigns running in parallel. The first campaign will target prospective patients searching online for information. The second will target caregivers. Each campaign will run simultaneously and will each be comprised of their own search engine ads/ results and dedicated landing page both geared specifically towards their respective target audience. The ads and their associated landing page/website will be selected and displayed automatically based on the keywords/search terms entered by an individual user online as well as the age of individual searching. The campaign will be accessible both via desktop and mobile.

Version Date: 6.9.22 Page 10 of 31

For each campaign, a landing page will be developed with the primary goal of facilitating treatment initiation for individuals with FEP and their caregivers searching for information online in NYS. In order to optimize website visibility, the landing page will focus on core messages derived from our initial evaluations that were found to be most relevant to information seeking individuals. These include accurately identifying and understanding early signs and symptoms of psychosis and finding local support. The landing page content will be driven by ETP staff along with input from Strong365's development team. Additional input will be obtained from existing ETP participants with lived FEP experience.

The campaign website page will offer:

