12. STATISTICAL ANALYSIS

- Describe how your data will be used to test the hypotheses.
- State clearly what variables will be tested and what statistical tests will be used.
- *Include sample size calculations.*
- If this is a pilot study, state which variables will be examined for hypothesis generation in later studies.

A stepped-wedge cluster randomization (CR) design will be implemented. After a baseline period of six months, two clusters (grouped clinics) will be randomly assigned in month 7 and by month 18, all of NYS will be running the campaign. This strategy allows each region to serve as its own control³⁷. The treatment effect can be modeled as a random effect at the cluster level which will accommodate treatment heterogeneity across the clinics. We grouped the 21 OTNY sites into 6 clusters based on geolocation as well as the total number of FEP referrals at each clinic between 10/01/2017 to 09/30/2018. We combined some regions to ensure that each cluster will be able to successfully meet recruitment criteria. The six clusters are; 1) Bronx, 2) Manhattan, 3) Queens, 4) Brooklyn, 5) Hudson River/Central NY, 6) Staten

Version Date: 6.9.22 Page 12 of 31

Island/Long-Island/Western NY. There will be a total of four 6-month time periods, including the baseline period where all 6 clusters receive the control treatment. All analyses for Aim 1 (hypotheses A and B) will be conducted within the Generalized Linear Mixed Models (GLMM) framework with an identity link for continuous outcomes and logit link for binary outcomes. Analyses for Aim 2 will be done using asymptotic z-tests for proportions after accounting for the variance inflation factors (VIF). Aim 3 is exploratory, and hence only 95% confidence intervals, accounting for VIFs, will be calculated for the rates.

Aim 1: Evaluate the effectiveness of a search engine ad campaign on reducing DUP and raising rates of FEP referrals by directly comparing DUP and FEP referrals pre and post campaign activation. Hypothesis A: Patients admitted to OTNY via campaign channels will demonstrate a significantly shorter DUP than those admitted to OTNY through traditional outreach prior to campaign activation.

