Aim 2: Determine the efficacy of a campaign targeting caregivers in promoting treatment initiation by comparing rates of OTNY enrollment arriving through the caregiver campaign to rates of enrollment arriving through the patient campaign. Hypothesis: Engaging caregivers online will significantly increase the likelihood of promoting treatment initiation of individuals with FEP as compared to engaging prospective patients alone.

Throughout the campaign, one dedicated landing page for each unique target audience (prospective patients and caregivers), will be promoted online, presenting each audience with a unique and identifiable campaign phone line, email, text line, and live chat options. We will compare rates of inquiries, number of FEP referrals, and number of patients admitted to OTNY throughout NYS arriving through the caregiver campaign to rates of inquiries, number of FEP referrals, and number of patients admitted to OTNY arriving through the participant campaign. Both campaigns will run in parallel and

Version Date: 6.9.22 Page 14 of 31

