each will target a dedicated audience based on demographics (age) and online search query. For example, "I am hearing voices" will generate the participant ad/campaign, while "my daughter is acting strange" will generate an entirely different set of ads geared towards caregivers. Power Analysis: Current OTNY referral data suggest that caregivers including parents are 5 times more likely to initiate a referral inquiry as compared to prospective participants themselves. We therefore anticipate that at least 2/3 (66.7%) of campaign referrals (approximately 20 weekly) will be generated by the parent campaign. Based on OTNY referral data, we anticipate that 20% will be appropriate and all will be enrolled into OTNY. Sample size necessary to detect a prevalence of 66.7% for the caregiver campaign compared to the null hypothesis of equal rates for the two campaigns is 68, which has to be multiplied by the design effect (variance inflation factor), [1 + (n-1)p], to get required sample size. As ICC (p) ranges from 0.01 to 0.06, the design effect will range from 1.67 to 5.02 and the sample size required will vary from 114 to 342. Although there are 24 six-month time periods from all clusters (4 per cluster and 6 clusters, $4 \times 6 = 24$) based on the stepped wedge design for Aim 1, only 12 of them will have the campaign. Based on recent OTNY referral data, the number of enrolled subjects per cluster in a 6-month period varied from 26 to 34, with an average of approximately 30. Thus, we expect to have (30 x 12) 360 subjects enrolled from the campaign part of the stepped wedge design. This sample size will be sufficient to detect the hypothesized difference in rates (66.7% vs. 33.3%) at 80% power and α = 0.05, with an ICC as high as 0.06.

Aim 3: Explore which methods of online engagement are most effective at promoting treatment initiation by comparing rates of OTNY enrollment of individuals interacting with research staff via live chat or two-way video to rates of enrollment of individuals utilizing text, email, and/or phone alone. Hypothesis: individuals with FEP who engage via two-way video or live chat will be significantly more likely to initiate in-person contact compared to individuals with FEP who engage via text, email, and/or phone alone.

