14. DATA MANAGEMENT AND CONFIDENTIALITY

- Describe the data and specimens to be sent out or received. As applicable, describe:
 - What information will be included in that data or associated with the specimens?
 - Where and how data and specimens will be stored?
 - How long the data will be stored?
 - Who will have access to the data?
 - Who is responsible for receipt or transmission of data and specimens?
- Describe the steps that will be taken to secure the data during storage, use and transmission.

Clinical research material will be obtained through a variety of mechanisms. Participants may choose to complete our online demographic survey/needs assessment as well as the psychosis screener (PQ-B). Participants who choose to leave contact information will be contacted via their preferred method including email, phone, and text. Participants may also choose to interact with research staff directly via live chat and two way video available on our campaign website. All information gained from theses interactions will be recorded by research staff and kept confidential through Northwell REDcap. Any data collected in excel files will be stored on protected Northwell servers. Any notes and test results obtained as part of the engagement and referral process will be treated with the same stringent confidentiality as treatment as usual. Investigators will collect the results of the referral and eligibility assessment. Online activity including engagement with campaign advertisements and website will be tracked by Google analytics and sent to research staff on a weekly basis.

Study records that identify patients will be kept private. They will not be identified in study records or publications disclosed outside of the Northwell Health System, except as detailed below.

The information that is collected for research will be analyzed for many years and it is not possible to know how long this analysis and follow-up will take.

Version Date: 6.9.22 Page 17 of 31

Data from this research may be used in medical publications or presentations. The information will be de-identified so that individual participants cannot be recognized and the information will no longer be considered Protected Health Information (PHI).

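### Aim 2 tests the caregiver campaign's share of arrivals against 50% without fixing or adjusting for each campaign's advertising exposure, so unequal exposure could confound the result

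*Combined protocol and SAP*

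**What the plan says.** Section 11 describes two campaigns in parallel, one for prospective patients and one for caregivers: "Each campaign will run simultaneously and will each be comprised of their own search engine ads/ results and dedicated landing page". Which ads a person sees depends on the search terms entered and on age. Section 2 says that the researchers choose the keywords and create the ads.

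Section 12 defines Aim 2 as "comparing rates of OTNY enrollment arriving through the caregiver campaign to rates of enrollment arriving through the patient campaign", and then lists what will be compared: "We will compare rates of inquiries, number of FEP referrals, and number of patients admitted to OTNY throughout NYS arriving through the caregiver campaign", against the same items for the patient campaign. The test is a z-test for proportions, adjusted only for variance inflation. The power paragraph gives the sample size for a 66.7% caregiver share, "compared to the null hypothesis of equal rates for the two campaigns is 68", and inflates it for clustering.

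Section 2 states the purpose: "we aim to identify the campaign target audience most effective at promoting treatment initiation". The Aim 2 hypothesis in section 12 concerns the likelihood of treatment initiation. Sections 11 and 14 say that exposure data will be collected: "Online activity including engagement with campaign advertisements and website will be tracked by Google analytics and sent to research staff on a weekly basis". Aim 2 does not use them.

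**The concern.** The number of people who arrive through a search-ad campaign depends on how readily the audience acts and on how often the ads are shown and clicked. The second part depends partly on choices the study team makes for each campaign, such as keywords and budget. A 50% null is a fair test of which audience responds better only if exposure is equal. The one parity the plan states is that the campaigns run at the same time.

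Randomisation gives no protection. The stepped wedge decides when a cluster starts the campaign, not the mix of the two campaigns within it. If exposure differs, the raw share mixes audience response with advertising intensity, and a larger sample makes a misleading answer more certain. At stake is the statement about the most effective target audience. Aim 1, which holds the primary outcome, is not affected.

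**Working it through.** **1. The plan's own figure.** Inputs from section 12 (Aim 2 power analysis): share 0.667, null 0.5, 80% power, alpha 0.05 (sidedness not stated; two-sided reproduces).

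n = [(1.96 × 0.5 + 0.8416 × √(0.667 × 0.333)) / (0.667 − 0.5)]² = [(0.980 + 0.397) / 0.167]² = 67.95, so 68.

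A two-sample test of 66.7% against 33.3% gives 34 per group, also 68 in total. The design effect is 1 + 67 × ICC, which is 1.67 at ICC 0.01 and 5.02 at ICC 0.06. Then 68 × 1.67 = 113.6 (114) and 68 × 5.02 = 341.4 (342). The arithmetic is sound. It is that of a split of arrivals, with no denominator of impressions, clicks, visitors or contacts.

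**2. What the 66.7% consists of.** The plan expects about 20 of 30 weekly campaign referrals from the caregiver campaign, 20% of them appropriate and all of those enrolled. It gives no separate conversion figure for the patient campaign. If 20% applies to both (assumption), enrolments are 20 × 0.20 = 4 and 10 × 0.20 = 2 weekly, a share of 4/6 = 66.7%. Conversion per referral is then identical, and the whole planned difference is volume.

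**3. Control of exposure.** Sections 2, 11, 12 and 14 state no allocation of budget, bids, impressions or clicks between the campaigns, and no offset or covariate for them.

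**4. How far unequal exposure could move the test.** Assume that both campaigns yield the same enrolments per unit of exposure and that the caregiver campaign gets k times the exposure. Its expected share is s = k/(1 + k). The effective sample size is n_eff = N / design effect, and

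P(test favours caregivers) = 1 − Φ{[1.96 × √(0.25/n_eff) − (s − 0.5)] / √(s(1 − s)/n_eff)}.

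Two values of N are used:
- 360, the plan's figure (30 × 12 cluster-periods). It applies the usual OTNY intake as if all of it came through the campaigns.
- About 208, from the 4 campaign enrolments weekly expected in sections 8 and 12: 12 cluster-periods × 26 weeks × 4/6, assuming an even split over the six clusters.

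Worked case, k = 2, N = 360, ICC 0.06: s = 0.6667; n_eff = 360/5.02 = 71.7; (0.1157 − 0.1667)/0.0557 = −0.915; probability 82%.

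| Assumed exposure split (caregiver:patient) | N 360, ICC 0.06 (n_eff 71.7) | N 360, ICC 0.01 (215.6) | N 208, ICC 0.06 (41.4) | N 208, ICC 0.01 (124.6) |
|---|---|---|---|---|
| 50:50 | 2.5% | 2.5% | 2.5% | 2.5% |
| 55:45 | 13% | 31% | 9% | 20% |
| 60:40 | 39% | 84% | 25% | 61% |
| 2:1 | 82% | 99.9% | 58% | 97% |

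The splits are assumptions; the documents give none. The model is symmetric, so more exposure for the patient campaign would push the result the other way and could hide a real caregiver advantage.

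**The case against.** The strongest reply is that the plan speaks of rates of enrolment and of likelihood, and specifies tests for proportions. For Aim 3, section 12 uses the same phrase about rates of enrolment for conversion among people who engaged. If Aim 2 means enrolment per engaged contact, advertising volume does not mechanically decide the winner. This stands in part, because the wording can be read that way. But Aim 2 defines no denominator, lists raw counts, and is powered as a share of arrivals.

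Total yield is also a legitimate practical question. It can be reported as such, but it does not show that one audience is more effective unless it is set against the exposure that produced it.

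A reader might infer that the campaign with more ad money will simply win. The documents do not support that. They give no budgets, bids or impressions, and nothing indicates that these will be unequal. The plan has a basis for its 2:1 expectation that has nothing to do with advertising: caregivers are said to be 5 times as likely to start an inquiry. Enrolments need not rise in proportion to spend either, since ads appear only in response to matching searches.

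A reader might also infer that equal budgets, or enrolments per ad dollar, would settle the matter. They would not. Equal dollars buy unequal clicks when click prices differ, and a per-dollar measure rewards cheaper keywords even if both audiences convert identically after clicking.

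**Conclusion.** The point holds in a limited form. As planned, Aim 2 tests the caregiver share of arrivals and enrolments against 50%, between non-randomised campaigns whose exposure is neither fixed nor adjusted for. The result could be confounded by unequal exposure, and by itself it cannot identify the more effective audience or the greater likelihood of treatment initiation.

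The size and direction of any bias are unknown. The illustration shows that it need not be small: at an assumed 2:1 split with equal yield per unit of exposure, the false-win probability is 58% to 99.9%, depending on ICC and on whether N is 360 or about 208. Those figures rest on enrolment being proportional to exposure. They are not a forecast for this trial.

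**What to change.** In section 12, under Aim 2, define the measure as OTNY enrolments per landing-page click, or per engaged contact, by campaign and cluster-period, using the ad and website data already tracked. It can be analysed as a proportion, or as a count model with log(clicks) as offset, with allowance for clustering. Because users are invited to return to the page, clicks count visits rather than people, which favours the count model for that denominator.

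In the Aim 2 power paragraph, restate the null as equal enrolment per click (or contact) and redo the sample size on that measure. Report impressions, clicks and spend by campaign. Give raw counts and enrolments per ad dollar as descriptive secondary measures only, and do not interpret the raw share against 50% as audience effectiveness. Equal budgets are not required.

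The cost is wording plus an export of clicks and spend by campaign, cluster and period, with no new patient data. The stated power may become less favourable. For scale, detecting 20% against an assumed 30% enrolment per referral, with referrals split 2:1, needs 224 + 448 = 672 referrals before inflation for clustering (two-sided 5%, 80% power). The comparison also remains non-randomised. It removes the effect of differing click or contact volume, not differences between the people who click.

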4. OBJECTIVE(S)/SPECIFIC AIMS AND HYPOTHESES

- A concise statement of the goal(s) of the current study.
- *The rationale for and specific objectives of the study.*
- The goals and the hypothesis to be tested should be stated.

Aim 1: Evaluate the effectiveness of a search engine ad campaign on reducing DUP and raising rates of FEP referrals by directly comparing DUP and FEP referrals pre-campaign to DUP and FEP referrals during the campaign. Hypothesis A: Patients admitted to OTNY via campaign channels will demonstrate significantly shorter DUP than those admitted to OTNY through traditional outreach prior to campaign activation. Hypothesis B: Activating the campaign will significantly increase the number of FEP referrals and patients admitted to OTNY as compared to the number of FEP referrals and patients to OTNY admitted pre-campaign activation.

Version Date: 6.9.22 Page 6 of 31

Aim 2: Determine the efficacy of a campaign targeting caregivers in promoting treatment initiation by comparing rates of OTNY enrollment arriving through the caregiver campaign to rates of enrollment arriving through the patient campaign. Hypothesis: Engaging caregivers online will significantly increase the likelihood of promoting treatment initiation for individuals with FEP as compared to engaging prospective patients online. Aim 3: Explore which methods of online engagement are most effective at promoting treatment initiation by comparing rates of OTNY enrollment of individuals with FEP interacting with research staff via two-way video and live chat to rates of enrollment of individuals with FEP utilizing text, email, and/or phone alone. Hypothesis: Individuals with FEP who engage via two-way video and live chat will be significantly more likely to initiate in-person contact compared to individuals with FEP who engage via text, email, and/or phone alone.

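### Aim 2 hypothesises a higher likelihood of treatment initiation, but the only test it quantifies is of the caregiver campaign's share of enrollees, so the 80% power statement covers yield and not likelihood

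*Combined protocol and SAP*

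**What the plan says.** Section 4 gives the Aim 2 hypothesis as "Engaging caregivers online will significantly increase the likelihood of promoting treatment initiation for individuals with FEP as compared to engaging prospective patients online". Section 12 repeats it almost word for word: "Engaging caregivers online will significantly increase the likelihood of promoting treatment initiation of individuals with FEP as compared to engaging prospective patients alone".

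Other parts of Aim 2 are closer to a comparison of volume. The aim sentence speaks of "comparing rates of OTNY enrollment arriving through the caregiver campaign to rates of enrollment arriving through the patient campaign", with no denominator. The planned comparisons are rates of inquiries, "number of FEP referrals, and number of patients admitted to OTNY throughout NYS arriving through the caregiver campaign", and the same quantities for the patient campaign.

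The opening of section 12 assigns Aim 2 to large-sample z-tests for proportions with a variance inflation factor. It does not say which proportion is tested.

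The Aim 2 power analysis starts from the statement that "caregivers including parents are 5 times more likely to initiate a referral inquiry as compared to prospective participants themselves" and concludes that "at least 2/3 (66.7%) of campaign referrals (approximately 20 weekly) will be generated by the parent campaign". It adds that "we anticipate that 20% will be appropriate and all will be enrolled into OTNY". The calculation itself is for the "Sample size necessary to detect a prevalence of 66.7% for the caregiver campaign compared to the null hypothesis of equal rates". It gives 68, inflated to between 114 and 342 for an ICC of 0.01 to 0.06. The plan judges this achievable with 360 enrolled subjects and restates the effect as 66.7% against 33.3%.

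**The concern.** Likelihood of treatment initiation for individuals with FEP is a conditional probability: of those engaged through a campaign, how many enrol. The powered quantity is different: of those who enrolled, how many came through the caregiver campaign. Everyone in that denominator has already enrolled, so the share cannot by itself estimate a probability of enrolling. It depends on how many people each campaign reaches as well as on how many of them go on to enrol.

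Section 2 lists, among the study's purposes, finding the target audience most effective at promoting treatment initiation. If the share test is significant and the conclusion follows the hypothesis as worded, a difference in inquiry volume could be reported as evidence that caregivers are more likely to bring a patient into care. The plan states neither a hypothesised difference nor power for that claim.

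**Working it through.** **1. The plan's 68.** Inputs from the Aim 2 power analysis: share 2/3 under the alternative, 1/2 under the null, 80% power, α = 0.05 (two-sided reproduces the figure).

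n = [(1.96 × √(0.5 × 0.5) + 0.842 × √(2/3 × 1/3)) / (2/3 − 1/2)]² = 68.2.

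A two-sample test of 66.7% against 33.3% gives 34.1 per group, again 68.2 in total, because the two figures are complements. The formula therefore cannot show which test was meant. The text can: 66.7% is introduced as a share of referrals, and 33.3% is the remainder.

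**2. Inflation.** The plan's design effect uses 68 as the cluster size: 1 + 67 × 0.01 = 1.67 and 1 + 67 × 0.06 = 5.02. Then 68 × 1.67 = 113.6 and 68 × 5.02 = 341.4, which match 114 and 342 after rounding up.

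**3. Power of the share test at 360.** Power = Φ[((1/6) × √(N/DE) − 1.96 × 0.5) / √(2/9)].
- DE 5.02: effective N = 71.7, power 82%.
- DE 1.67: effective N = 215.6, power 99.9%.

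So the 80% statement is met for the share.

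**4. What the share says about likelihood.** Weekly campaign referrals are 30 (section 12, Hypothesis B), of which about 20 come from the caregiver campaign, leaving 10. Suppose 20% are appropriate and all of those enrol, in both campaigns:
- enrollees: 20 × 0.20 = 4 and 10 × 0.20 = 2;
- caregiver share: 4/6 = 66.7%;
- enrolment per referral: 20% and 20%; per FEP referral: 100% and 100%.

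The powered alternative then arises with no difference in likelihood. As an illustration only, if caregiver referrals converted at 15% and patient referrals at 20%, the share would be (20 × 0.15)/(20 × 0.15 + 10 × 0.20) = 3/5 = 60%, still above one half.

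**5. How many campaign enrollees.** The 360 is 30 × 12 cluster-periods, with 30 taken from recent OTNY enrolment per cluster and period. The share is defined only among people arriving through a campaign. Hypothesis B expects 4 such enrolments a week. Twelve cluster-periods over six clusters are two statewide-equivalent periods of 26 weeks, so 4 × 26 × 2 = 208, or 17.3 per cluster-period. With ICC 0.06:
- plan's DE of 5.02: effective N = 41.4, power 58%;
- DE from 17.3 per cluster-period, 1 + 16.3 × 0.06 = 1.98: effective N = 105, power 94%.

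**6. What a likelihood test could detect.** Assumptions: 6 FEP referrals a week × 52 weeks = 312, split 2:1 as 208 and 104; overall enrolment 4/6 = 67%.

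Standard error = √(0.667 × 0.333 × (1/208 + 1/104)) = 0.0566.
- Normal multiplier 2.80, no clustering: 2.80 × 0.0566 = 0.159, about 16 points.
- Multiplier 3.51 (t with 5 df for six clusters): 3.51 × 0.0566 = 0.199, about 20 points.

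Overall enrolment of 50% to 80% moves the first figure between 16.8 and 13.5 points.

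**The case against.** The strongest reply is that Aim 2 is about yield and that one word in the hypothesis is loose. The aim sentence, the counts of referrals and admissions by campaign, and the power analysis all fit a yield comparison, and the phrase about promoting treatment initiation can be read at campaign level. The planned counts would also let anyone compute enrolment per referral. Much of this stands, and it is why the remedy is mainly rewording. It does not remove the mismatch: the hypothesis says likelihood in both sections, and the tested proportion is never defined.

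Three stronger readings are tempting, and the documents do not support them.
- *The 80% power figure is wrong.* It reproduces for the share if 360 campaign enrollees are available.
- *The test has a false-positive rate of 82% or more.* That is its intended power for yield. It becomes an error only if a significant share is reported as higher likelihood.
- *The plan itself assumes equal conversion in the two campaigns.* The sentence on 20% being appropriate directly follows the one on the caregiver campaign's 20 weekly referrals and may refer only to those. The equal-conversion example is therefore conditional. Its all-enrolled assumption also differs from Hypothesis B, where 4 of 6 appropriate referrals enrol.

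The inference that a share test will be run comes from the power analysis. The methods paragraph would equally allow a two-sample test of enrolment proportions, which is a further reason to define the proportion.

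**Conclusion.** The point holds as a mismatch between the worded hypothesis and the powered quantity. The sample-size arithmetic is sound for the caregiver campaign's share, with at least 82% power at 360 campaign enrollees under the plan's design effects. It says nothing about likelihood, for which the plan gives neither an effect nor power.

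The 80% also depends on 360 being campaign-channel enrollees. At 208, power for the share at ICC 0.06 is about 58% or about 94%, depending on the cluster size used in the design effect. A likelihood comparison per FEP referral could detect about 16 points before clustering and about 20 with 5 df, given the assumed volumes, the 2:1 split and 67% enrolment.

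This should be fixed, but its reach is limited: it concerns the Aim 2 conclusion only, and section 12 names Hypothesis A as the primary outcome.

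**What to change.** 1. In sections 4 and 12, restate the Aim 2 hypothesis and its conclusion as campaign yield, meaning the share of OTNY enrollees arriving through each campaign. Define that proportion where section 12 names the z-test.
2. In the Aim 2 power analysis, say that the 80% applies to the share only and is conditional on 360 campaign-channel enrollees. Give the power at about 208 as well.
3. Report enrolment per FEP referral, and per unique inquiry, by campaign, with cluster-adjusted 95% confidence intervals. Label these as a non-randomised association, because audiences are set by age and search query.

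If likelihood is to remain the tested hypothesis, define it as enrolment per FEP referral by campaign and replace the power statement with a detectable difference of the size shown above.

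The cost is a few sentences and a small added analysis. Contact lines are campaign-specific and admissions are already recorded. The added rates need a rule for counting each prospective patient once, since users may return repeatedly, and a rule for unknown enrolment status, since section 24 makes re-contact subject to permission. The downside of the yield option is that its result reflects audience size and search volume and cannot show that caregivers convert better. The likelihood option would have less power than the plan now states.
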